4.6.2. Per Protocol (PP) Population

All patients in the Evaluable Patients Population without major protocol deviations.

Sensitivity analyses for the primary and key secondary endpoint will be undertaken for the PP population.

Below are the examples of major protocol violations that will exclude patients from the PP population:

- No written informed consent
- No evidence of hypersensitivity reactions/silent inactivation to PEG-ASNase.
- Investigational Medicinal Product (IMP) non-safety related issues that led to delaying or skipping eryaspase dose; these include, but not limited to: RBC cross match incompatibility, IMP delivery issues, other logistical issues.

Sponsor:	NOPHO – Nordic Society of Pediatric Hematology & Oncology		
Protocol:	NOR-GRASPALL 2016		
Document Version No.:	2.0	Document Date:	14-May-2021

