7.6 Dose interruption and modification

Temporarily dose interruption in case of following:

- Severe hepatic impairment (transaminases >10 times ULN).
- Bilirubin > ULN and other clinical signs of SOD (according to the PdL consensus definitions)
- Serious infectious disease

Treatment can be resumed when parameters are normalized and the clinical condition allows further treatment. Impact of hematological parameters will not induce dose interruption.

Eryaspase treatment is discontinued in case of:

- Clinical allergy of any grade
- Pancreatitis
- Serious hemorrhage or serious thrombosis
- No asparaginase activity

There will be no dose-modification due to haematological or non-hematological toxicities only temporarily dose interruption or discontinuation of the eryaspase treatment.

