8.4.1 Total Asparaginase Activity

Blood samples will be drawn to determine asparaginase activity as follows:

Courses with dose every 2 weeks:

- 15 min (\pm 5 min) before eryaspase administration
- End of infusion (0-10 min)
- 24 hours post-infusion (\pm 2 hrs)
- 3 days (\pm 1 day) post-infusion
- 6 days (\pm 1 day) post-infusion
- 10 days (\pm 2 days) post-infusion
- 14 days (\pm 2 days) post-infusion. The 14-day post-infusion sampling corresponds with the pre-eryaspase for next dose (i.e., the Day 15 sample for dose 1 = the pre-dose sample for dose 2, etc.)

Courses with dose every 6 weeks:

- 15 min (\pm 5 min) before eryaspase administration
- End of infusion (0-10 min)
- 24 hours post-infusion (\pm 2 hrs)
- 3 days (\pm 1 day) post-infusion
- 6 days (\pm 1 day post-infusion
- 10 days (\pm 2 days) post-infusion

- 14 days (\pm 2 days) post-infusion
- 21 days (\pm 2 days) post-infusion

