2.3. Primary Endpoint

The primary endpoint is the percentage of patients with asparaginase (ASNase) activity >100 U/L at 14 days following the *first* infusion (nadir).

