2.4. Secondary Endpoints

2.4.1. Pharmacokinetic Evaluation:

2.4.1.1. Key Secondary Endpoint:

- The percentage of patients with ASNase activity >100 U/L at 14 days following the *fourth* infusion of the 2-week dosing intervals.

Sponsor:	NOPHO – Nordic Society of Pediatric Hematology & Oncology		
Protocol:	NOR-GRASPALL 2016		
Document Version No.:	2.0	Document Date:	14-May-2021

2.4.2. Pharmacodynamic Evaluation:

- Cerebrospinal fluid (CSF) concentrations of asparagine (ASN), aspartate (ASP), glutamine (GLN), and glutamate (GLU)

2.4.3. Immunogenicity:

- Anti-asparaginase antibodies.

2.4.4. Safety and Tolerability:

- Incidence of hypersensitivity (allergic reactions and silent inactivation);
- Adverse events from start of treatment until 30 days after last administration;
- Levels of cytotoxic methotrexate (MTX polyglutamates) and 6 mercaptopurine metabolites (6 thioguanine nucleotides (6TGN) and methylated metabolites (MeMP)) and of DNA-TGN levels in circulating leukocytes.

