3. STUDY DESIGN

3.1. Synopsis of Study Design

This is a single arm, multicenter, multinational study to assess the pharmacological activity, safety and immunogenicity of eryaspase in combination with the NOPHO ALL 2008 or ALLTogether pilot protocol chemotherapy administered as second line treatment to children or adult patients from 1 to 45 years old with ALL who experience hypersensitivity reactions (clinical allergic reaction or silent inactivation) to PEG-ASNase.

All patients will receive the NOPHO ALL 2008 or ALLTogether pilot protocol chemotherapy regimen, which consists of an induction treatment, consolidation, delayed intensification phase, maintenance phases, a CNS prophylaxis and interim maintenance for a total of 30 months' treatment duration. Once a patient presents with hypersensitivity to PEG- ASNase, eryaspase will be given as a replacement therapy for remaining scheduled PEG-ASNase administrations, Figure 1, **Figure 2**.

Eryaspase will be administered every two weeks for a maximum of four doses, and then administered every 6 weeks for three doses to the end of planned treatment according to the NOPHO ALL 2008 protocol. For patients in the ALLTogether pilot protocol, eryaspase will be administered every 2 weeks for a maximum of 7 doses. The duration of treatment with eryaspase will be dictated by the remaining number of intended courses following the occurrence of hypersensitivity to PEG-ASNase, and therefore it may range between 1-7 doses of eryaspase.

[figure not shown]
Assessments include overall safety profile of eryaspase, PK/PD parameters of eryaspase, immunogenicity of eryaspase, during successive courses of treatment with eryaspase.

Primary trial assessments for each patient will continue for one month following the end of the planned eryaspase treatment phases (approximately 6 months in case of 7 doses). Each patient will receive treatment in about 22 months after last administration of eryaspase according to the NOPHO ALL 2008 or ALLTogether pilot protocol. After cessation of therapy, patients will be followed for recurrence of disease or the development of late effects. The follow-up after cessation of therapy should be done according to guidelines on each country and site, but no assessments of those will be included for this study.

Sponsor:	NOPHO – Nordic Society of Pediatric Hematology & Oncology		
Protocol:	NOR-GRASPALL 2016		
Document Version No.:	2.0	Document Date:	14-May-2021

[figure not shown]

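### The per-protocol set has no time limit on dose-delay exclusions, so events after the primary Day-14 sample can remove patients and may bias that sensitivity analysis against the drug

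*SAP*

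**What the plan says.** SAP 2.3 fixes the primary endpoint early: "The primary endpoint is the percentage of patients with asparaginase (ASNase) activity >100 U/L at 14 days following" the first infusion. The key secondary endpoint in SAP 2.4.1.1 is the same measure after the fourth infusion at two-week intervals.

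SAP 4.6.1 makes the Evaluable Patients (EP) set the primary population: everyone with a Day-14 (± 2 days) value after the first dose. SAP 4.6.2 takes the PP set from it by removing major deviators, and states: "Sensitivity analyses for the primary and key secondary endpoint will be undertaken for the PP population". One PP set thus serves both endpoints. The exclusions are introduced with "Below are the examples of major protocol violations that will exclude patients from the PP population", and the third example is "Investigational Medicinal Product (IMP) non-safety related issues that led to delaying or skipping eryaspase dose", illustrated by cross-match incompatibility, delivery failures and other logistics. No dose number or cut-off date is attached.

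Three other provisions bear on this:

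- Protocol 8.4.1, for two-week courses: "The 14-day post-infusion sampling corresponds with the pre-eryaspase for next dose".
- SAP 3.1, on treatment length: "therefore it may range between 1-7 doses of eryaspase".
- Protocol 7.6 lists "No asparaginase activity" among the reasons for discontinuing eryaspase. Protocol 11.1 lists lack of activity as a possible reason for stopping.

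**The concern.** A PP set should leave out patients whose deviation could have distorted the measurement being analysed. Here the rule reaches past the measurement. A bag that fails cross-match at dose 5 says nothing about activity two weeks after dose 1, but as written it takes the patient out of the primary PP analysis.

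The loss may also depend on the outcome. Someone stopped after dose 1 for absent activity has no later dose to be delayed and cannot be excluded on that ground. Someone with good activity goes on to further doses and remains exposed to the rule. PP is the only alternative analysis population the SAP names for the primary endpoint. If it departs from the EP result, readers will take the main finding as fragile when the cause may be late logistics.

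**Working it through.** **1. The plan's own figure.** SAP 4.1 gives 49 evaluable patients, 50% versus 70%, one-sided 2.5%, exact binomial, 80% power. With n = 49 the test rejects at 32 or more responders: P(X ≥ 32 | 0.5) = 0.022 and P(X ≥ 32 | 0.7) = 0.810. Recruitment is 49/0.9 = 54.4, rounded up to 55. Both figures reproduce.

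**2. Timing.** The Day-14 sample after dose 1 is also the sample before dose 2. With 1 to 7 doses per patient, 0 to 6 doses fall after the primary measurement. A delay to dose 2 might shift a draw that is tied to that dose, but a draw outside the ± 2-day window leaves the patient out of EP, and so out of PP already. For a patient with an in-window value, delays to doses 2-7 come too late to change it. This step needs no assumption.

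**3. Size of a possible bias.** The documents give no delay rate, so q (risk of a logistical delay or skip per later dose) is an assumption. Let p be the true rate, m the number of later doses in successes, and f the share of failures that stop after dose 1; the other failures have the same m.

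- Share of successes kept: S = (1 − q)^m
- Share of failures kept: F = f + (1 − f)·S
- PP rate = p·S / [p·S + (1 − p)·F]

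With p = 0.70 (the SAP alternative) and m = 3 (assumed):

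| q | S | all failures stop (f = 1) | half stop (f = 0.5) | equal exposure (f = 0) |
|---|---|---|---|---|
| 2% | 0.941 | 0.687 | 0.694 | 0.700 |
| 5% | 0.857 | 0.667 | 0.683 | 0.700 |
| 10% | 0.729 | 0.630 | 0.663 | 0.700 |

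Worked cell, q = 10%, f = 1: 0.7 × 0.729 = 0.510, and 0.510/(0.510 + 0.300) = 0.630.

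The result depends on m. With m = 6, the most the plan allows, and f = 1, the PP rate is 0.674, 0.632 and 0.554 for the same three values of q. With m = 0 there is no effect.

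**4. Loss of patients without bias.** With equal exposure, q = 5% and m = 3, the expected PP size is 49 × 0.857 = 42. Seven patients go although their primary measurement is sound.

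**5. How few exclusions matter.** One-sided exact p against 50%:

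- 32/49: p = 0.022, which meets 2.5%. Drop one success: 31/48, p = 0.030, which does not.
- 33/49: p = 0.011. Drop three successes: 30/46, p = 0.027.

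**The case against.** A reader might infer that the rule strips out successes and keeps failures, so that the PP analysis is necessarily biased. The documents do not support that:

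- The stop is for absent activity, not for a value at or below 100 U/L. A patient with low but measurable activity fails the endpoint and may continue, with later doses that can be delayed.
- The Day-14 sample goes to a central laboratory (Protocol 8.4), no turnaround time is stated, and each dose is ordered five working days ahead (Protocol 7.4.3). A failure can meet a dose-2 supply problem before anyone knows it is a failure.
- Clinical allergy also ends treatment but is not an endpoint failure. A success who reacts at dose 2 stops with little later exposure, which works the other way.
- The planned number of doses depends largely on treatment protocol, risk group and when hypersensitivity occurred.

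A reader might also infer that the primary endpoint is left with no usable sensitivity analysis. SAP 6.2.3 plans a dose-adjusted analysis and subgroup forest plots, and SAP 2.5 adds a 400 U/L threshold. Nor does a downward bias make the PP result worthless: a PP result that still clears 50% would support the main result despite it.

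Finally, the SAP calls its exclusions examples, and SAP 4.14 has the sponsor or designee decide, violation by violation and before hard lock, whether exclusion is warranted. That leaves room to disregard late delays.

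These points stand as limits on how much can be claimed. They do not remove the defect. The listed item excludes as worded, and SAP 4.14 neither ties the decision to the endpoint's timing nor requires it to be made without sight of the Day-14 values.

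**Conclusion.** The concern holds in a limited form. As written, the PP rule removes patients from the primary sensitivity analysis for events that follow the measurement and cannot affect it. That at least costs patients needlessly. It may also bias the PP rate downward, against the drug, if failures receive fewer later doses than successes. The stop for absent activity makes this plausible; nothing in the documents shows that it occurs.

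The size cannot be derived from the documents. The figures above rest on an assumed 2-10% risk per dose, three later doses in successes and a true rate of 70%. With equal later exposure the bias is zero.

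The confirmatory test in the EP population is untouched. What is at stake is a PP result that disagrees with it for reasons unrelated to activity. For the key secondary endpoint, delays to doses 2-4 come before the measurement and are proper grounds for exclusion; only later delays are a problem there. This is an inexpensive improvement, not a threat to the primary conclusion.

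**What to change.** In SAP 4.6.2, define the PP set separately for each endpoint and count only deviations that occur up to that endpoint's Day-14 sample: after infusion 1 for the primary, after infusion 4 for the key secondary. Add that deviations are classified without knowledge of the Day-14 results, and carry this into the violation file described in SAP 4.14.

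Later delays then cannot remove anyone from the primary PP analysis, and bias from this source is zero. If no earlier deviation occurs, the PP analysis keeps all 49 patients and the 0.81 power.

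The cost is one SAP sentence and a second PP flag in the analysis data. No data collection and no primary analysis changes.

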1.1 Investigational Product

1.1.1 ERYASPASE (GRASPA[®]), new formulation of L-asparaginase
Eryaspase is a dispersion of homologous erythrocytes encapsulating recombinant L-asparaginase for infusion.

Additional descriptive information can be found in the Investigator's Brochure (IB).

[figure not shown]

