2.1.2 Potential Risks for the Patients

Adverse effects resulting from the administration of asparaginase or erythrocytes are well known. Toxicity data come from clinical studies carried on since 2005 with eryaspase as add-on therapy with protocols combining several chemotherapies that have their own toxicity profile.

In study GRASPALL 2009-06, the incidence of allergic reactions was in both eryaspase arms in the non-allergic (7.7%) and allergic patients (11.5%). There were no withdrawals due to hypersensitivity reactions, either in the allergic or non-allergic patient subsets. The most common drug-related events with eryaspase were hypofibrinogenemia (26.9%), asymptomatic pancreatitis (26.9%), elevated transaminases (19.2%), hypoalbuminemia (15.4%), and decreased anti-thrombin III (11.5%).

The risk of asparaginase related toxicities is not increased compared to the treatment with other formulations of asparaginase e.g. PEG-asparaginase.

Detailed safety information is summarized in the Investigator Brochure.

The risk of transfusion complications are very low when national guidelines for blood transfusions are followed, the risk rate is 3.7/100000 transfusions of red blood cells which include transfusion with incorrect blood components.(24)

The patients will not have any inconvenience and risk because of extra hospital visits, blood tests, lumbar punctures for CSF collecting and clinical assessments because it all will be done according to the conventional investigations in the NOPHO ALL 2008 or ALLTogether pilot protocol.

Previous studies have shown a good safety profile and the risk of toxicity is not increased compared to the conventional treatment with PEG-asparaginase. According to that it is assessed that getting eryaspase and completing the asparaginase treatment are beneficial compared to the risk. The risk is considered reasonable in proportion to the severity of the diagnosis and the conventional treatment according to the NOPHO ALL 2008 or ALLTogether pilot protocol.

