5.4 Exclusion Criteria

1. Philadelphia chromosome positive ALL.
2. Participation in another clinical trial interfering with the study therapy with exception of NOPHO ALL-2008 or ALLTogether pilot protocol. Patients can participate in other clinical trials not interfering with the study drug. In case of doubt this is assessed by the PI.
3. Uncontrolled intercurrent illness including, but not limited to, patients receiving combination antiretroviral therapy or patients with severe or systemic infection, or psychiatric illness/social situations that would limit compliance with study requirements.
4. Other severe acute/chronic medical or psychiatric condition or laboratory abnormality that may increase the risk associated with study participation or study drug administration, or may interfere with the interpretation of study results, and in the judgment of the investigator would make the patient inappropriate for entry into this study.
5. Pregnant or lactating females. (serum human chorionic gonadotropin pregnancy test at screening). Use of a highly effective contraceptive measure in women of child-bearing potential and sexually active girls that are of child-bearing potential is required (contraceptive measures are specified in section 6.0).
6. Inadequate organ functions, which prohibit further asparaginase administration;
 - a) History of pancreatitis
 - b) History of serious hemorrhage or serious thrombosis with prior asparaginase therapy
 - c) Severe hepatic impairment at the time of administration (bilirubin >3 times ULN, transaminases >10 times ULN)
 - d) Pre-existing known coagulopathy (e.g. haemophilia)
6. History of grade 3 or higher transfusion reactions or any contraindication to receive blood transfusion. Presence of specific anti-erythrocytes antibodies (auto-antibodies or anti-public antibodies) preventing from getting a compatible packed Red Blood Cells for the patient.

7. Patient under concomitant treatment likely to cause hemolysis.

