7.4.3 Dispensing/Allocation of ERYASPASE

Once a patient has consented and is determined to be eligible for this study, ERYTECH Pharma must be notified and the process below followed:

To initiate eryaspase manufacturing and allocation of eryaspase, NOPHO or designee must be provided with the documents listed below:

- **At Screening:** a validated phenotype and ABO status (double determination is mandatory), as well as IAST results are required. The blood group form should be completed, and the lab results should be attached to this form. A template of the blood group form along with instructions is available in IMP Manual.
- **5 working days prior to each eryaspase injection:** Prescription Sheet indicating patient identifiers, weight, and estimated time of delivery. A template of the prescription sheet is available in IMP Manual.

- **Within 72 hours of each eryaspase injection:** Documentation of the IAST (Irregular Antibody Screening Test) performed at the local immuno-hematology laboratory.
- **In case of positive IAST** or previous history of positivity, a compatibility test is mandatory in order to appropriately select the packed Red Blood Cells. In cases of a positive IAST where compatibility testing is required, the administration of eryaspase may be delayed depending on the timeline for the compatibility results.

Instructions for blood sampling management sent to French blood bank (EFS) for selecting compatible packed Red Blood Cells are detailed in IMP Manual.

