9.2 Day 1 of each eryaspase administration (± 2 days)

1. Physical examination if clinician finds it necessary.
2. Perform and record vital signs (temperature, blood pressure, pulse rate) and weight.
3. Evaluate Karnofsky/Lansky score
4. Evaluate ALL Clinical Assessment according to the normal procedure at the centers.
5. Record any AEs/SAEs
6. Record any newly added concomitant medications
7. Collect blood for PK/PD testing
8. Collect blood for Antibodies Titers
9. IAST Results within 72 hours prior to each administration
10. Administer eryaspase via IV 150 IU/kg

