- Anemia: Anemia, hemoglobin decreased
- Thrombocytopenia: Thrombocytopenia, platelet count decreased
- Leukopenia: Leukopenia, white blood cells count decreased
- Leukocytosis: Leukocytosis, white blood cells count increased
- Hyperglycemia/Diabetes: Hyperglycemia, Diabetes mellitus, Diabetes mellitus inadequate control, Type 2 diabetes mellitus, blood glucose level increased
- Hypertriglyceridemia: Hypertriglyceridemia, triglycerides increased
- Hepatotoxicity: Liver injury, drug-induced liver injury, hepatocellular injury, Venoocclusive liver disease
- Hyperuricemia: Hyperuricemia, blood uric acid increased
- Hypokalemia: Blood potassium decreased, hypokalemia
- Hyponatremia: Blood sodium decreased, hyponatremia
- Hypocalcemia: Blood calcium decreased, hypocalcemia
- Pancreatitis: Pancreatitis, Acute pancreatitis
- Biochemical pancreatitis: Lipase increased, Amylase increased, pancreatic enzymes increased
- Drug hypersensitivity reaction: Drug hypersensitivity, hypersensitivity, anaphylactic reaction, anaphylactic shock, erythema multiform, edema, dermatitis allergic, face edema
- 4. Other allergic reaction: Rash, Erythema multiform, Food allergy, Anaphylactic shock, Transfusion reactions, Angioedema, allergic transfusion reaction.

All AEs and SAEs will be collected and reported in the patient's eCRF throughout study duration (i.e. for time subject signs the informed consent and until 30 days after last administration of eryaspase or chemotherapy. All AEs along with the coded terms will be listed.

The following general rules apply to adverse events:

Sponsor:	NOPHO – Nordic Society of Pediatric Hematology & Oncology		
Protocol:	NOR-GRASPALL 2016		
Document Version No.:	2.0	Document Date:	14-May-2021

- TEAEs are defined as those AEs that started on or after the first dose of study medication or that worsened after the first dose of study medication and with an onset date occurring during the treatment period.
- Treatment period is defined from the first dosing day of study treatment (minimum of the first dosing day for eryaspase (Day 1) until 30 days after last dose of study treatment (maximum of the last dosing day for eryaspase). This includes the safety follow-up period as well.
- If an AE is reported for a given patient more than once during treatment, the worst severity and the worst relationship to study treatment will be tabulated.

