8.2. Laboratory Data

Clinical laboratory values will be expressed using SI units. Local laboratories are being used for this clinical study for hematology and blood chemistry. For each individual laboratory used, laboratory reference ranges and units are collected. Reference ranges will be entered into the local laboratory normal range.

The laboratory collection CRFs (hematology and serum chemistry) include fields for additional, non-protocol-required clinically significant laboratory tests, including laboratory test name, result, units, normal range low, and normal range high.

NCI CTCAE version 5 will be used for grading applicable laboratory tests.

Standard biological assessments will be performed at the local laboratory of the Investigator's site at selection, before any eryaspase administration as follows:

- Hematology: complete blood count (CBC);
- Serum Biochemistry: lactate dehydrogenase (LDH), bilirubin, alanine aminotransferase (ALT), aspartate transaminase (AST), gamma glutamyl transpeptidase (GGT), alkaline phosphatase (ALP), albumin, potassium and calcium;
- Coagulation: fibrinogen, antithrombin III (ATIII), partial thromboplastin time (PTT), and prothrombin time.

Sponsor:	NOPHO – Nordic Society of Pediatric Hematology & Oncology		
Protocol:	NOR-GRASPALL 2016		
Document Version No.:	2.0	Document Date:	14-May-2021

The actual value and change from baseline on each study evaluation will be summarized for each clinical laboratory parameter. Baseline is defined as the last value taken prior to the date and time of first dose. In the event of repeat values, the last non-missing value per study day/time will be used.

Shift tables will be performed on laboratory abnormalities of the highest NCI CTCAE grade or the worst severity if there is no NCI CTCAE grade. Shifts from baseline will be classified as improved from baseline, no change from baseline, or worsened from baseline.

All laboratory data will be provided in data listings. A subset listing will be presented for all clinically significant abnormal laboratory values. This listing will present all laboratory values for any parameter with at least one clinically significant abnormal value so that a time course for that lab parameter can be presented.

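### The SAP plans no summary of the red-cell antibody screens and crossmatches done before every infusion, labels crossmatch incompatibility non-safety, and groups all transfusion reactions with allergy

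*SAP*

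**What the plan says.** **The product and the tests.** Protocol 1.1.1: "Eryaspase is a dispersion of homologous erythrocytes encapsulating recombinant L-asparaginase for infusion". The protocol's Study Overview (5.1) foresees 1 to 7 doses per patient. Protocol 9.2 lists "IAST Results within 72 hours prior to each administration" for each dosing day. Protocol 7.4.3 asks that the sponsor or its designee receive, within 72 hours of each injection, "Documentation of the IAST (Irregular Antibody Screening Test) performed at the local immuno-hematology laboratory", and says that a positive screen can delay the dose. Protocol 7.4.4 requires a compatibility test before each infusion, recorded on the Shipment and Administration Form. Note g to Protocol Table 2, repeated under SAP Table 1, ties the crossmatch to safe administration.

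**Eligibility and stated risk.** Protocol 5.4 excludes "Presence of specific anti-erythrocytes antibodies (auto-antibodies or anti-public antibodies) preventing from getting a compatible packed Red Blood Cells for the patient". Protocol 2.1.2 states: "The risk of transfusion complications are very low when national guidelines for blood transfusions are followed".

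**The SAP.** Safety variables (4.5.2), the laboratory panel (8.2) and immunogenicity (4.5.1, 6.4) name neither the IAST nor the crossmatch; the only antibodies analysed are those against asparaginase. SAP 4.6.2 excludes from the per-protocol (PP) set patients with product "non-safety related issues that led to delaying or skipping eryaspase dose; these include, but not limited to: RBC cross match incompatibility", along with delivery and other logistical problems. SAP 8.1 defines one adverse event group as "Other allergic reaction: Rash, Erythema multiform, Food allergy, Anaphylactic shock, Transfusion reactions, Angioedema, allergic transfusion reaction".

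**The concern.** The tests exist because the carrier is a donor cell and because some patients may have, or acquire, antibodies against such cells. An incompatibility first found after infusion 1 could be a response to the product, yet SAP 4.6.2 places it with shipping faults. A reader of the report who asks how many patients developed a new red-cell antibody, how many infusions were incompatible, or how many doses were late or missed for that reason would find no planned answer.

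The grouping in SAP 8.1 raises a second problem. It names transfusion reactions in general as well as allergic ones, so the general term brings non-allergic reactions into an allergy group. Allergic reactions are part of the hypersensitivity incidence that SAP 2.4.4 lists as a secondary endpoint and Protocol 4.1 lists among the primary endpoints. The SAP does not say which adverse event groups feed that incidence, so the pooling could carry into it.

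**Working it through.** The plan states no figure on this point. The check is a reading of the protocol's tests against every SAP section that could report them, followed by the precision that a summary would have.

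**1. Routes by which results could reach the report**

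- *Tables.* No SAP section plans a table of IAST or crossmatch results. The discontinuation reasons in SAP 5.1 have no category for incompatibility.
- *Listings of CRF data (SAP 4.11).* These cover what is on the CRF, and SAP 4.2 bases the primary analyses on cleaned eCRF data. Protocol 9.1 expressly puts the screening IAST on the CRF. For later infusions, Protocol 8.1 only gives a general instruction to register all data in the CRF, while the stated destination of IAST results is the sponsor's designee or the manufacturer (7.4.3; Table 2, note f), and crossmatch checks go on a separate form (7.4.4). Presence in the database is possible but not assured.
- *Deviation listing (SAP 4.14).* It would show a dose delayed or skipped for incompatibility if logged as a deviation. It gives no rate, and it misses a new antibody for which a compatible unit was found in time.
- *Adverse events (SAP 8.1).* Protocol 10.0 keeps events judged unrelated to eryaspase off the CRF. A symptomless new antibody need not be entered as an event at all.

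**2. The label.** Protocol Table 2, note g: the crossmatch is done so that the product can be given safely. SAP 4.6.2: a failed crossmatch is a non-safety matter. The SAP repeats note g under its own Table 1, so it also disagrees with itself.

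**3. Precision of a summary.** Inputs: n = 50 (Protocol 12.6) or n = 55 (SAP 4.1). Assumption: every patient has a negative baseline and at least one later screen. A patient with a single infusion may have no later screen, so the real denominator may be smaller and the limits wider.

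Exact two-sided 95% upper limit for zero events: 1 − 0.025^(1/n).

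- n = 50: 1 − 0.025^(1/50) = 7.1%
- n = 55: 1 − 0.025^(1/55) = 6.5%

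The documents give no rate for new red-cell antibodies. For assumed true rates p, the chance of at least one case is 1 − (1 − p)^n:

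| p | n = 50 | n = 55 |
|---|---|---|
| 1% | 39.5% | 42.5% |
| 2% | 63.6% | 67.1% |
| 5% | 92.3% | 94.0% |

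The trial could thus plausibly see a case at rates of a few per cent, and could not exclude such rates if it saw none. Both facts call for a stated count and interval.

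**The case against.** The strongest reply is that nothing is hidden. CRF data, protocol deviations and adverse events are all listed; the Safety Population (SAP 4.6.3) is every dosed patient; PP exclusion touches only sensitivity analyses of two activity endpoints; and the bullet in 4.6.2 sorts causes of late or missed doses rather than classifying harms. No objective or endpoint concerns red-cell antibodies, and the output shells are in a separate document.

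Much of this stands, and it rules out several stronger readings:

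- *That new antibodies would go unreported.* Individual cases could appear by the routes above. What is missing is a summary and any assurance that the per-infusion results are in the database.
- *That affected patients leave the safety tables.* They do not.
- *That a haemolytic event would be counted as allergy.* The group in SAP 8.1 does not name haemolysis, the tables by system organ class and preferred term may still show the specific term, and SAP 8.2 summarises blood count, LDH and bilirubin. The supportable point is narrower: transfusion reactions of any kind are pooled with allergy in that grouping.
- *That this harm is specific to eryaspase, or complicates later transfusions.* Protocol 6.3 allows ordinary transfusions, which also bring donor cells, and the documents say nothing about later transfusions.
- *That red-cell antibodies as such bar entry.* They do so only when they prevent a compatible unit; Protocol 7.4.3 provides for patients with a positive screen. Nor does every incompatibility mean a new antibody: note g provides for incompatibility testing whatever the IAST result.
- *That the expected number can be read from Protocol 2.1.2.* Its 3.7 per 100,000 transfusions, applied to a ceiling of 50 × 7 = 350 infusions, gives 350 × 3.7/100,000 = 0.013. That rate covers transfusion complications, including incorrect blood components, and does not measure antibody formation.

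The reply does not remove the conflict over the label, the mixed grouping, or the lack of any count from tests required before every infusion.

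**Conclusion.** The point holds as a gap in safety reporting of moderate weight. The SAP leaves screens and crossmatches without a count, a rate or a link to dosing. Its non-safety label conflicts with the protocol's reason for the crossmatch and must be reconciled. Its allergy group mixes allergic with other transfusion reactions. The primary endpoint, its test, the sample size and the Safety Population do not change.

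The size of the clinical risk is unknown. All that can be stated is precision: zero new antibodies in 50 or 55 patients would still be compatible with rates up to 7.1% or 6.5%, if every patient has a negative baseline and a later screen. The conclusion also assumes that the unseen output shells do not already add such a table.

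**What to change.** 1. **SAP 8.1.** Give transfusion reactions, including haemolysis, their own group; keep only allergic transfusion reactions with allergy.
2. **SAP 8.2, Safety Population.** Add one table with: patients with a new positive IAST after a negative baseline (last result before infusion 1), with an exact 95% confidence interval and the denominator of patients who had a later screen; patients positive at baseline, shown separately; crossmatch incompatibilities; and doses delayed or skipped because of them. Confirm that the per-infusion results are in the database.
3. **SAP 4.6.2.** List crossmatch incompatibility apart from delivery and logistical problems, without the non-safety label, and state whether such patients stay excluded from the PP set.

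**Cost.** The tests are already required, so no new sampling is needed. Per-infusion results may have to be transferred from IAST reports and Shipment and Administration Forms and reconciled with the eCRF. Because ordinary transfusions are allowed, a conversion cannot be attributed to eryaspase alone; a footnote should say so and give concomitant transfusions where recorded. The protocol requires concomitant medications to be recorded but does not expressly name transfusions, so that record should be checked first.
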